7.7.1 Subject Disposition

Subject disposition will be summarized by treatment group and will include subjects that enrolled, were randomly assigned, discontinued, and completed the study. For discontinued subjects, the reasons for discontinuation will be summarized.

7.7.2 Analyses of Demographic and Baseline Characteristics

Demographic and baseline characteristics such as age, sex, race, body weight, height, BMI, and medical history will be summarized by treatment group using descriptive statistics.

7.7.3 Analysis of Primary Endpoint

The primary endpoint is the mean change from baseline in DAS28-hsCRP at Week 12 which is based on 3 individual components including TJC, SJC and hsCRP (see calculation in Appendix 13.6).

The mean change from baseline in DAS28-hsCRP at Week 12 between each of the active treatment groups and the placebo arm will be analyzed using an analysis of covariance (ANCOVA). The difference in mean change from baseline between each active treatment and the placebo will be estimated and the corresponding 95% CI and p-value will be calculated.

The primary endpoint will be analyzed using the ITT, mITT, and PP analysis sets. For the mITT set, results for subjects that are missing at Week 12 will be imputed using the last observation carried forward (LOCF) method.

A sensitivity analysis based on the 4-component DAS28-hsCRP (consisting of 4 individual components including TJC, SJC, hsCRP, and subject's global assessment of disease activity [VAS]; see calculation in Appendix 13.6) will be performed on the ITT set restricted to subjects who consistently completed the subject's global assessment of disease activity reverse VAS scale.

7.7.4 Analysis of Secondary Endpoints

For secondary endpoints, change from baseline will be analyzed at Weeks 2, 4, 8, and 12 using a mixed model repeated measures (MMRM) analysis. The Chi-square tests will be used to compare the ACR20, ACR50, and ACR70 rates between the active treatment and placebo groups at Weeks 2, 4, 8, and 12. The median hsCRP will be summarized descriptively.

The DAS28-related secondary endpoint is based on 3 individual components including TJC, SJC and hsCRP (see calculation in Appendix 13.6). Sensitivity analyses based on the 4-component DAS28-hsCRP (consisting of 4 individual components including TJC, SJC, hsCRP, and subject's global assessment of disease activity [VAS]; see calculation in Appendix 13.6) will be performed using the ITT set restricted to subjects who consistently completed the subject's global assessment of disease activity reverse VAS scale.

All secondary endpoints will be analyzed using the ITT and PP analysis sets. The ACR20, ACR50, and ACR70 will be also analyzed using the mITT set, where results for subjects that are missing at the relevant visit will be imputed using nonresponder imputation (NRI).

For analyses on ACR responses (ACR20, ACR50 and ACR70) described above, the analysis will be performed on the subjects assessment of arthritis pain and physician global assessment of disease activity VAS scales, using the same approach as the sensitivity analysis on 4-component DAS28-hsCRP to identify the subjects to be included in this analysis set.

For the analyses on the other VAS-related secondary endpoints (ie, the individual assessments using VAS), using the same approach as the sensitivity analysis on 4-component DAS28-hsCRP, only subjects who completed the corresponding individual VAS assessment consistently will be included.

7.7.5 Safety Analyses

Continuous parameters (such as laboratory measurements, ECG results, and vital signs) will be summarized separately for each treatment at each nominal time point using descriptive statistics (mean, SD, minimum, median, and maximum).

Discrete parameters (such as AEs, concomitant medications, and physical examination results) will be summarized separately for each treatment at each nominal time point using frequency counts and percentages. All safety data will be listed.

7.7.6 Pharmacokinetic Analyses

Plasma concentrations of SKI-O-592 and its metabolites (M2 and M4) will be listed and summarized separately for each treatment and day at each nominal time point using descriptive statistics (number of observations [n], mean, SD, coefficient of variation [CV], minimum, median, and maximum). Individual and mean plasma concentration versus time profiles will be plotted for each treatment and day.

PK parameters for SKI-O-592 and its metabolites will be calculated using noncompartmental methods. Descriptive statistics (n, geometric mean, geometric CV, mean, SD, CV, minimum, median, and maximum) for the PK parameters for SKI-O-592 and its metabolites will be presented for each treatment and day. Treatment comparisons will be performed as deemed appropriate.

7.7.7 Pharmacodynamic Analyses

Absolute and percentage change from baseline in the percentage of activated gp53/CD63+ basophils in peripheral blood will be listed and summarized separately for each treatment and day at each nominal time point using descriptive statistics (n, mean, SD, CV, minimum, median, and maximum). Individual and mean absolute and percentage change from baseline in the percentage of activated gp53/CD63+ basophils will be plotted versus time for each treatment and day.

PD parameters for the percentage of activated gp53/CD63+ basophils will be calculated using noncompartmental methods. Descriptive statistics (n, mean, SD, CV, minimum, median, and maximum) for the PD parameters will be presented for each treatment and day. Treatment comparisons will be performed as deemed appropriate.

7.7.8 Exploratory PK/PD Analysis

Individual and mean plasma concentrations of SKI-O-592, M2 and M4 will be plotted versus change from baseline in the percentage of activated gp53/CD63+ basophils in peripheral blood on Day 1 and at Week 12.

Exploratory PK/PD modeling may also be performed; full details will be provided in the statistical analysis plan.

7.7.9 Interim Analyses

There is no interim analysis planned for this study.

8 Data Quality Assurance

This study will be conducted according to the ICH E6(R2) risk and quality processes described in the applicable procedural documents. The quality management approach to be implemented in this study will be documented and will comply with the current ICH guidance on quality and risk management (ICH 2005).

8.1 Data Management

As part of the responsibilities assumed by participating in the study, the Investigator agrees to maintain adequate case histories for the subjects treated as part of the research under this protocol. The Investigator agrees to maintain accurate eCRFs and source documentation as part of the case histories. These source documents may include diary cards, laboratory reports, and ECG strips.

Study site personnel will enter subject data into Medidata Rave. The analysis data sets will be a combination of these data and data from other sources (eg, laboratory data).

Clinical data management will be performed in accordance with applicable sponsor standards and data cleaning procedures to ensure the integrity of the data, eg, removing errors and inconsistencies in the data. Adverse events and concomitant medication terms will be coded using MedDRA Version 20.0 or later, an internal validated medication dictionary.

After database lock, each study site will receive a CD-ROM containing all of their site specific eCRF data, as entered into Medidata Rave for the study, including full discrepancy and audit history. Additionally, a CD-ROM copy of all of the study site's data from the study will be created and sent to the sponsor for storage. PPD will maintain a duplicate CD-ROM copy for their records.

In all cases, subject initials will not be collected or transmitted to the sponsor.

9 Ethics

9.1 Independent Ethics Committee or Institutional Review Board

Federal regulations and the ICH guidelines require that approval be obtained from an IRB/IEC before participation of human subjects in research studies. Before study onset, the protocol, informed consent, advertisements to be used for the recruitment of study subjects, and any other written information regarding this study to be provided to the subject or the subject's legal guardian must be approved by the IRB/IEC. Documentation of all IRB/IEC approvals and of the IRB/IEC compliance with ICH harmonised tripartite guideline E6(R2): Good Clinical Practice (GCP) will be maintained by the site and will be available for review by the sponsor or its designee.

All IRB/IEC approvals should be signed by the IRB/IEC chairman or designee and must identify the IRB/IEC name and address, the clinical protocol by title or protocol number or both, and the date approval or a favorable opinion was granted.

The Investigator is responsible for providing written summaries of the progress and status of the study at intervals not exceeding 1 year or otherwise specified by the IRB/IEC. The Investigator must promptly supply the sponsor or its designee, the IRB/IEC, and, where applicable, the institution, with written reports on any changes significantly affecting the conduct of the study or increasing the risk to subjects.

9.2 Ethical Conduct of the Study

The study will be performed in accordance with the ethical principles that have their origin in the Declaration of Helsinki, ICH GCP, and all applicable regulations.

9.3 Subject Information and Consent

A written informed consent in compliance with the respective applicable regulatory authority regulations shall be obtained from each subject before entering the study or performing any unusual or nonroutine procedure that involves risk to the subject. An informed consent template may be provided by the sponsor to study sites. If any institution-specific modifications to study-related procedures are proposed or made by the site, the consent should be reviewed by the sponsor or its designee or both before IRB/IEC submission. Once

reviewed, the consent will be submitted by the Investigator to his or her IRB/IEC for review and approval before the start of the study. If the ICF is revised during the course of the study, all active participating subjects must sign the revised form.

Before recruitment and enrollment, each prospective subject or his or her legal guardian will be given a full explanation of the study and be allowed to read the approved ICF. Once the Investigator is assured that the subject/legal guardian understands the implications of participating in the study, the subject/legal guardian will be asked to give consent to participate in the study by signing the ICF.

The Investigator shall retain the signed original ICF(s) and give a copy of the signed original form to the subject or legal guardian.

10 Investigator's Obligations

The following administrative items are meant to guide the Investigator in the conduct of the study but may be subject to change based on industry and government standard operating procedures, working practice documents, or guidelines. Changes will be reported to the IRB/IEC but will not result in protocol amendments.

10.1 Confidentiality

All laboratory specimens, evaluation forms, reports, and other records will be identified in a manner designed to maintain subject confidentiality. All records will be kept in a secure storage area with limited access. Clinical information will not be released without the written permission of the subject (or the subject's legal guardian), except as necessary for monitoring and auditing by the sponsor, its designee, the US FDA, or the IRB/IEC.

The Investigator and all employees and coworkers involved with this study may not disclose or use for any purpose other than performance of the study any data, record, or other unpublished, confidential information disclosed to those individuals for the purpose of the study. Prior written agreement from the sponsor or its designee must be obtained for the disclosure of any said confidential information to other parties.

10.2 Financial Disclosure and Obligations

Investigators are required to provide financial disclosure information to allow the sponsor to submit the complete and accurate certification or disclosure statements required under 21 Code of Federal Regulations (CFR) 54. In addition, the Investigator must provide to the sponsor a commitment to promptly update this information if any relevant changes occur during the course of the investigation and for 1 year following the completion of the study.

Neither the sponsor nor PPD is financially responsible for further testing or treatment of any medical condition that may be detected during the screening process. In addition, in the absence of specific arrangements, neither the sponsor nor PPD is financially responsible for further treatment of the subject's disease.

10.3 Investigator Documentation

Prior to beginning the study, the Investigator will be asked to comply with ICH E6(R2) 8.2 and Title 21 of the CFR by providing the following essential documents, including but not limited to:

- IRB/IEC approval
- Original investigator-signed investigator agreement page of the protocol
- Form FDA 1572, fully executed, and all updates on a new fully executed Form FDA 1572
- Curriculum vitae for the investigator and each subinvestigator listed on Form FDA 1572
- Financial disclosure information to allow the sponsor to submit complete and accurate certification or disclosure statements required under 21 CFR 54. In addition, the Investigators must provide to the sponsor a commitment to promptly update this information if any relevant changes occur during the course of the investigation and for 1 year after the completion of the study.
- IRB/IEC-approved informed consent, samples of site advertisements for recruitment for this study, and any other written information regarding this study that is to be provided to the subject or legal guardian
- Laboratory certifications and normal ranges for any local laboratories used by the site, in accordance with 42 CFR 493

10.4 Study Conduct

The Investigator agrees that the study will be conducted according to the principles of ICH E6(R2). The Investigator will conduct all aspects of this study in accordance with all national, state, and local laws or regulations. Study information from this protocol will be posted on publicly available clinical trial registers before enrollment of subjects begins.

10.5 Adherence to Protocol

The Investigator agrees to conduct the study as outlined in this protocol in accordance with ICH E6(R2) and all applicable guidelines and regulations.

10.6 Adverse Events and Study Report Requirements

By participating in this study the Investigator agrees to submit reports of SAEs according to the timeline and method outlined in the protocol. In addition, the Investigator agrees to submit annual reports to the study site IRB/IEC as appropriate.

10.7 Investigator's Final Report

Upon completion of the study, the Investigator, where applicable, should inform the institution; the Investigator/institution should provide the IRB/IEC with a summary of the study's outcome and the sponsor and regulatory authority(ies) with any reports required.

10.8 Records Retention

Essential documents should be retained until at least 2 years after the last approval of a marketing application in an ICH region and until there are no pending or contemplated marketing applications in an ICH region or at least 2 years have elapsed since the formal discontinuation of clinical development of the study drug. These documents should be retained for a longer period, however, if required by the applicable regulatory requirements or by an agreement with the sponsor. It is the responsibility of the sponsor to inform the Investigator/institution as to when these documents no longer need to be retained.

10.9 Publications

After completion of the study, the data may be considered for reporting at a scientific meeting or for publication in a scientific journal. In these cases, the sponsor will be responsible for these activities and will work with the Investigators to determine how the manuscript is written and edited, the number and order of authors, the publication to which it will be submitted, and other related issues. The sponsor has final approval authority over all such issues.

Data are the property of the sponsor and cannot be published without prior authorization from the sponsor, but data and publication thereof will not be unduly withheld.

11 Study Management

11.1 Monitoring

11.1.1 External Data Monitoring Committee

No external data monitoring committee is planned for the study.

11.1.2 Monitoring of the Study

The clinical monitor, as a representative of the sponsor, has the obligation to follow the study closely. In doing so, the monitor will visit the Investigator and study site at periodic intervals, in addition to maintaining necessary telephone and letter contact. The monitor will maintain current personal knowledge of the study through observation, review of study records and source documentation, and discussion of the conduct of the study with the investigator and personnel.

All aspects of the study will be carefully monitored, by the sponsor or its designee, for compliance with applicable government regulation with respect to current GCP and current standard operating procedures. A risk-based approach to data monitoring in line with ICH E6(R2) will be utilized for this study.

11.1.3 Inspection of Records

Investigators and institutions involved in the study will permit study-related monitoring, audits, IRB/IEC review, and regulatory inspections by providing direct access to all study records. In the event of an audit, the Investigator agrees to allow the sponsor, representatives of the sponsor, or a regulatory agency (eg, FDA) access to all study records.

The Investigator should promptly notify the sponsor and PPD of any audits scheduled by any regulatory authorities and promptly forward copies of any audit reports received to the sponsor.

11.2 Management of Protocol Amendments and Deviations

11.2.1 Modification of the Protocol

Any changes in this research activity, except those necessary to remove an apparent, immediate hazard to the subject, must be reviewed and approved by the sponsor or its designee. Amendments to the protocol must be submitted in writing to the Investigator's IRB/IEC for approval before subjects can be enrolled into an amended protocol.

11.2.2 Protocol Deviations

The Investigator or designee must document and explain in the subject's source documentation any deviation from the approved protocol. The Investigator may implement a deviation from, or a change of, the protocol to eliminate an immediate hazard to study subjects without prior IRB/IEC approval. As soon as possible after such an occurrence, the implemented deviation or change, the reasons for it, and any proposed protocol amendments should be submitted to the IRB/IEC for review and approval, to the sponsor for agreement, and to the regulatory authorities, if required.

A deviation from the protocol is an unintended or unanticipated departure from the procedures or processes approved by the sponsor and the IRB/IEC and agreed to by the Investigator. A significant deviation occurs when there is nonadherence to the protocol by the subject or Investigator that results in a significant, additional risk to the subject. Significant deviations can include nonadherence to inclusion or exclusion criteria, enrollment of the subject without prior sponsor approval, or nonadherence to FDA regulations or ICH GCP guidelines and will lead to the subject being withdrawn from the study (Section 4.2).

Protocol deviations will be documented by the clinical monitor throughout the course of monitoring visits. Principal Investigators will be notified in writing by the monitor of deviations identified during a monitoring visit. If a protocol deviation occurs (or is identified) after a subject has been enrolled, the principal investigator is responsible for notifying IRB/IEC/regulatory authorities (as applicable), as well as their site monitor.

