1.4 Placebo Rationale

The proposed study is a placebo-controlled, double-blind study of oral SKI-O-703 coadministered with background therapies for RA. The double-blind, placebo-controlled, randomized clinical study design is considered the gold standard for the safety and efficacy assessment of a new therapy both by clinicians and regulatory authorities. In this study subjects will be allowed to receive background medications for RA, including MTX, and other oral DMARDs, therefore subjects are also allowed to receive permitted concomitant medications in line with current standard of care (SOC) practices for RA. Any subject who cannot adhere to the protocol or who discontinues treatment will have an end-of-treatment (EOT) and will be followed for the intended duration of the study.

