4.2 Withdrawal of Subjects From the Study Treatment and/or the Study

4.2.1 Reasons for Withdrawal/Discontinuation

Subjects may withdraw from the study at any time and for any reason without prejudice to their future medical care by the investigator or at the study site. Every effort should be made to keep subjects in the study. The reasons for subjects not completing the study will be recorded.

A subject may be withdrawn from the study for any of the following reasons:

1. Noncompliance with the protocol.
 - Protocol violations may result in data that are not deemed evaluable (by the investigator) for a protocol analysis and/or may require subject(s) to be discontinued.
2. Pregnancy.
 - If a female subject becomes pregnant, she must discontinue study drug immediately.
3. A serious or intolerable adverse event(s) (AE[s]) that in the Investigator's opinion requires withdrawal from the study.
 - Upon occurrence of a serious or intolerable AE that in the investigator's opinion requires withdrawal from the study, the investigator will confer with the sponsor.
 - If a subject is discontinued because of an AE, the event will be followed until it is resolved.
4. Laboratory safety assessments that reveal clinically significant hematological or biochemical changes from the baseline values.
5. Symptoms or an intercurrent condition not consistent with the protocol requirements or that justifies withdrawal (eg, development of contraindications of use of study drug).
6. Lost to follow-up.
 - Subjects that are considered lost to follow-up, reasonable attempts must be made to obtain information on the final status of the subject.

- At a minimum, 2 phone calls must be made and 1 certified letter must be sent for documentation.

7. Death of the subject.
8. Early termination of the study by the sponsor.
9. The subject withdraws consent.

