4.2.2 Handling of Withdrawals

Subjects who discontinue study treatment or active participation in the study will no longer receive study drug. When a subject withdraws from the study, the reason(s) for withdrawal shall be recorded by the investigator on the relevant page of the eCRF. Whenever possible, all subjects who discontinue study drug or withdraw from the study prematurely will undergo all end-of-study assessments.

Subject who choose to discontinue study drug treatment but continue to participate in the study should complete end of treatment visit as soon possible, preferably within 2 weeks. Afterwards, subjects should follow the regular visit schedule and adhere to all study procedures except for dispensing study drug and blood sample collection for optional exploratory research and validation studies.

Subjects who fail to return for final assessments will be contacted by the site in an attempt to have them comply with the protocol. Following a minimum of 2 documented unsuccessful telephone calls, a registered letter will be sent to the subject in a final attempt to ensure protocol compliance.

It is vital to obtain follow-up data on any subject withdrawn because of an AE or serious AE (SAE). In every case, efforts must be made to undertake protocol-specified, safety, follow-up procedures.

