8.2.1. Primary Analysis

The primary analysis will be conducted on observed cases, which means DAS28-hsCRP at Week 12 will be calculated only when all the three individual components (TJC28, SJC28 and hsCRP) are assessed at this visit; otherwise, DAS28-hsCRP at Week 12 will be considered as missing.

The change from baseline in DAS28-hsCRP at visit Week 12 will be analyzed using an analysis of covariance (ANCOVA) model. The model will include treatment groups as a factor and DAS28-hsCRP at baseline as a covariate. Within-group least-square (LS) means and the associated standard errors (SE), the treatment differences in LS means and the associated SEs, the 2-sided 95% CIs, the 2-sided p-values for treatment comparisons between each of active treatment group and placebo group, and the 2-sided p-values for treatment comparisons among active treatment groups (high dose vs. low dose) will be estimated and provided. Descriptive statistics of baseline, observed value and change from baseline at Week 12 will be summarized by treatment group.

The primary efficacy analyses will be performed based on the ITT set, and then repeated using the PP set.

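### Protocol 11.2.2 makes withdrawal from the study mandatory after a significant deviation, against Sections 4.2.1 and 1.4, and a dosed subject withdrawn this way before Week 12 has no value in the primary analysis

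*Protocol*

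**What the plan says.** Protocol 11.2.2 defines a significant deviation as nonadherence, by the subject or the Investigator, that results in significant additional risk to the subject. It gives examples: "Significant deviations can include nonadherence to inclusion or exclusion criteria, enrollment of the subject without prior sponsor approval", and departures from FDA regulations or GCP. It then states that such deviations "will lead to the subject being withdrawn from the study" and refers to Section 4.2.

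Three other parts of the protocol bear on this:

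- **Section 4.2.1**, inside the section that 11.2.2 cites, is permissive: "A subject may be withdrawn from the study for any of the following reasons". Noncompliance with the protocol is the first reason listed. The same section says "Every effort should be made to keep subjects in the study".
- **Section 1.4** says that a subject who cannot adhere to the protocol, or who stops treatment, has an end-of-treatment visit and "will be followed for the intended duration of the study".
- **Section 4.2.2** covers, among others, subjects who choose to stop study drug but stay in the study: "Afterwards, subjects should follow the regular visit schedule and adhere to all study procedures except for dispensing study drug".

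In the SAP, Section 8.2.1 states "The primary analysis will be conducted on observed cases", so all three DAS28-hsCRP components must be present at Week 12. SAP 4.2 assigns the Visit 5 EOT record to Week 12 only for subjects who completed the treatment period. For everyone else it is an early-termination visit.

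**The concern.** A site that finds a significant deviation after dosing has three instructions: it must withdraw the subject (11.2.2), it may do so (4.2.1), or, where the subject cannot adhere, the subject is followed to the planned end (1.4). Different sites could act differently in the same situation.

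What is at stake is primary-endpoint data. If the mandatory rule is followed, a subject who is taking study drug and attending visits could leave before Week 12, even because of an Investigator's fault. The missing value would then result from a rule in the protocol and not from the subject's choice. The analysis does not need this, because the PP set already excludes subjects with major deviations.

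**Working it through.** **1. The passages side by side**

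| Place | Who | Instruction |
|---|---|---|
| Protocol 11.2.2 | Significant deviation (subject or Investigator, significant added risk) | Withdrawal from the study is mandatory |
| Protocol 4.2.1 | Noncompliance, among other reasons | Withdrawal is possible; retention is the aim |
| Protocol 1.4 | Subject who cannot adhere, or who stops treatment | End-of-treatment visit, then follow-up to the planned end |
| Protocol 4.2.2 | Subject who stops drug but stays in the study | Regular visits continue without dispensing |

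The first row conflicts with the second on whether withdrawal is required. It conflicts with the third where the significant deviation is the subject's own nonadherence. The fourth row does not conflict, since it applies to subjects who remain in the study. It does show that stopping drug and leaving the study are separable. Protocol 6.8 makes the same separation for pregnancy.

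**2. What happens to the Week 12 value**

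- Protocol 4.2.3: subjects who received at least one dose are not replaced.
- Protocol 4.2.2: subjects who withdraw have end-of-study assessments where possible. Under SAP 4.2 an early Visit 5 EOT record does not count as Week 12.
- SAP 8.2.1: without Week 12 components there is no Week 12 DAS28-hsCRP, and the primary analysis imputes nothing.
- SAP 4.5: the subject remains in the ITT set, which depends on randomisation and dosing.
- SAP 8.2.2 to 8.2.4: the subject enters the multiple-imputation analyses on the ITT set and, with a post-baseline assessment, the LOCF analysis on the mITT set. All are sensitivity analyses.

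**3. The plan's own sample size**

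Inputs from Protocol 7.4 and 7.7: difference 0.80, SD 1.25, two-sided 5% level, one-way ANOVA, four equal arms, 37 completers per arm, 10% drop-out.

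Overall F test with one arm differing by 0.80 (means 0, 0, 0, 0.8; grand mean 0.2):

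- Sum of squared deviations = 3 × 0.04 + 0.36 = 0.48
- Noncentrality = n × 0.48 / 1.25²
- n = 36: 11.06, power 0.794
- n = 37: 11.37, power 0.806

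So 37 per arm reproduces. For drop-out, 37 / 0.9 = 41.1, rounded up to 42 per arm; 4 × 42 = 168 = 148 + 20, which also reproduces.

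**4. Illustrative effect on power**

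The efficacy claims are pairwise against placebo, so the two-group t test is the relevant measure: noncentrality = 0.80 / (1.25 × √(2/n)), with 2n − 2 degrees of freedom. The extra loss rates are assumptions; neither document gives one.

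| Assumed extra loss | n per arm, from 37 | Power | n per arm, from 42 less 10% drop-out | Power |
|---|---|---|---|---|
| 0% | 37 | 0.775 | 37.8 | 0.784 |
| 5% | 37 × 0.95 = 35.15 | 0.753 | 42 × 0.85 = 35.7 | 0.760 |
| 10% | 37 × 0.90 = 33.3 | 0.730 | 42 × 0.80 = 33.6 | 0.734 |

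The starting value is below 0.80 because this is a pairwise test and not the overall F test. Section 11.2.2 does not cause that gap.

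**The case against.** The strongest reply is that 11.2.2 is a narrow safety provision. It covers only deviations that create significant added risk, and a stricter rule for that subset can sit beside a general list of permitted reasons. Its examples are mostly enrolment or site failures, whereas 1.4 concerns subjects who cannot adhere. The losses may be few and already inside the 10% drop-out allowance, since noncompliance is a listed withdrawal reason.

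Much of this stands. The risk qualifier limits the reach of the rule, the direct overlap with 1.4 is confined to nonadherence by the subject, and the numerical effect may be nil. Two things remain. Section 11.2.2 cites Section 4.2 as its basis, yet 4.2.1 does not make withdrawal mandatory. And added risk may bear on study drug, but it does not by itself explain ending data collection, which the protocol treats separately elsewhere.

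A reader might infer more than the documents support:

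- **That any deviation forces withdrawal.** The definition requires significant additional risk.
- **That the ITT set is broken.** Membership is unchanged; what is lost is a Week 12 observation, and only if withdrawal comes first.
- **That the treatment comparison is biased.** Eligibility failures predate randomisation in a double-blind trial, so no arm-related mechanism is shown for that class. Missingness that depends on later conduct is possible, but the documents do not show that it differs by arm.

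**Conclusion.** The inconsistency between 11.2.2 and Sections 4.2.1 and 1.4 is real and should be reconciled. Applied as written, the mandatory rule creates avoidable missing Week 12 data for dosed subjects withdrawn early, and only sensitivity analyses cover the gap.

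The size cannot be fixed from the documents. Under assumed extra losses of 5% or 10%, pairwise power falls by about 2 to 4.5 percentage points from 0.775. If these withdrawals are already counted in the planned drop-out, planned power does not change. These figures assume the plan's difference and SD, equal loss across arms and no gain from baseline adjustment. The sample size itself is not in error on this point. The firmer reasons to act are inconsistent handling across sites and missing data caused by a protocol rule; loss of power is secondary.

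**What to change.** Reconcile Protocol 11.2.2 with 4.2.1 and 1.4 so that a significant deviation does not by itself end scheduled data collection, including the Week 12 assessment. Decisions on study drug and subject safety stay with the sponsor's clinical team, and no clinical rule is proposed here.

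Also check the Visit 5 EOT rule in SAP 4.2. That folder serves both as Week 12 and as the early-termination visit, and no other visit mapping is done. A subject who is off drug but still in follow-up could attend at Week 12 and still have no value labelled Week 12. The SAP should state how that assessment is recorded and mapped.

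The cost is one reworded protocol sentence, plus a clarification of SAP 4.2 and, if needed, a way to capture the Week 12 record separately. The protocol change alone would clearly help subjects who would otherwise have completed treatment; those off drug need the SAP check as well.
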